25.1 Unique subject identifier

All the patients who sign the informed consent form for this study will be coded with "unique subject identifiers".

The unique subject identifier consists of the 5-digit screening number (e.g. S1001, S1002,...S10028 etc.), and, if applicable, the 4-digit subject clinical investigational number (e.g. 1001, 1002, etc.). Specifically, the first subject study number was referred to the study site.

Allocation screening number and subject clinical investigational number are separated by slashes (e.g. "S101/1001" for site number 1, "S201/2001" for site number 2, "S301/3001" for site number 3).

Study Sites	Screening Number	Subject Clinical Investigational Number
SITE Number 1	S1001, S1002, S1003,	1001, 1002, 1003, 1004,

Study code: 052/SI Hyalistil Bio PF Mono

P.O. San Marco, Azienda Ospedaliero Universitaria Policlinico "G. Rodolico - San Marco" Oculistica, [name], [name] (Italy) [contact] Email: [contact]	S1004, S1010, S1028etc.	etc.
SITE Number 2 U.O. di Oculistica, Presidio Belmonte, Azienda Ospedaliero Universitaria Policlinico "Paolo Giaccone" [name], [name] (Italy) [contact] Email: [contact]	S2001, S2002, S2003, S2004, S2028 etc.	2001, 2002, 2003, 2004, etc.

25.2 Coding dictionaries

Medical/surgical history and underlying diseases, physical examination abnormalities and AEs will be coded using the Medical Dictionary for Regulatory Activities (MedDRA™).

Prior and concomitant medications will be coded using the WHO Drug Dictionary Enhanced (WHODDE). Version of coding dictionaries will be stated in the SAP and the study report. Study Monitoring, Quality Control and Quality Assurance.

26 Monitoring, Data and Quality Management

26.1 Clinical monitoring and identification of source data

Monitoring is the act of overseeing the progress of a clinical trial and of ensuring that it is conducted, recorded and reported in accordance with the clinical investigation plan, SOPs, Good Clinical Practice (GCP), and the applicable regulatory requirement(s).

UNIFARM will designate qualified person(s) to maintain a close liaison with the Investigators and study staff to ensure the study is being conducted with respect to GCP and according to the approved clinical investigation plan and subsequent amendment(s).

This liaison will consist of documented visits and follow-up letters, and/or telephone call or Email communication, in accordance with monitoring plan, before the start of study and at regular intervals during the study to allow for the periodic reviews of the progress of the study.

UNIFARM is responsible to verify that all incidents have been transmitted to the Sponsor and to the Competent Authority and the Ethic Committee if deemed necessary.

Study code: 052/SI Hyalistil Bio PF Mono

The CRA will explain the clinical investigation plan and study related procedures to all study staff, including the Investigator. If new collaborators are included during the clinical investigation, additional training sessions will be organized by the Investigator and/or the CRA. The main responsibilities of the monitor CRA are to verify Investigators' adherence to the clinical investigation plan and that informed consent is obtained and recorded for all patients prior to implementation of any study procedure.

The nature and location of all source documents will be identified to ensure that all sources of original data required to complete the eCRF are known to the Sponsor and participating study-site personnel and are accessible for verification by the CRA.

The CRA will contact and visit the Investigator at regular intervals during the study. He will compare the eCRFs with medical records and other relevant documentation through direct access, during the on-site monitoring visits. He verifies the completeness, consistency and accuracy of the data being recorded in the CRF by the Investigator.

The Sponsor expects that, during any monitoring visits, the relevant participating study-site personnel will be available, the source documentation will be accessible, and a suitable environment will be provided for review of observational study-related documents.

The confidentiality of the subjects' identities shall be well protected consistent with local and national regulations when the source documents are subject to direct access.

The monitor will provide the Investigator with all the study materials before the study starts and, during the course of the study, will check at least the following:

- Full compliance with ICH-GCP, ISO 14155:2020, EU Regulation 745/2017, GDPR, the clinical investigation plan and applicable regulatory requirements;
- Subject recruitment;
- Subject compliance;
- Medical Device accountability;
- Completeness and accuracy of the eCRF data and their consistency with the source documents (appropriate source data verification will be conducted on all eCRFs);
- Verification of the facilities;
- Investigator's Site File.

The monitor will ensure completeness of eCRFs on an ongoing basis.

Study monitor will have access to all records (including source documents when applicable) necessary to ensure the integrity of the recorded data. During monitoring visits, the Investigators and authorized staff will assist the monitor to check the eCRFs and other documents pertinent to the project.

As part of the supervision of the study progress, other Sponsor personnel or the CRO may, on request, accompany the CRA on visits to the study site. The Investigator and his/her collaborators commit to cooperate with the CRA to resolve any problems, corrections or possible misunderstandings concerning the findings detected in the course of these monitoring visits.

26.2 Source Documents

Source documents are defined as original documents, data and records. This may include hospital

records, clinical and office charts, laboratory data/information, pharmacy dispensing and other records. Data collected during this study must be recorded on the appropriate source documents.

26.3 Audit

The audit is an independent verification, separate from the monitoring activity, of the activities and the documents to ensure that the activities pertinent to the study were duly carried out and that they were recorded, analyzed and transferred in compliance with the clinical investigation plan, GCP, relevant SOPs and with applicable legislation.

26.4 Inspections

Authorized representatives of national and foreign Competent Authorities may perform an official review of the study site, including, study site and source data verification. The purpose of inspection is to systematically and independently examine all study-related activities and documents, to determine whether these activities were conducted, and data were recorded, analysed, and accurately reported according to the clinical investigation plan, GCP, ICH guidelines, and any applicable regulatory requirements. The Investigator/Institution will contact immediately the Sponsor if contacted by a regulatory agency about an inspection at the study site.

25. Safety Data Evaluation

All safety data from medical examinations will be documented in the eCRFs, summarized by descriptive statistics and the results will be included in the clinical investigation Report.

26. Adherence to Clinical Investigation Plan

Except for an emergency situation in which proper care or medical treatment is required for protection, safety and well-being of the subjects, the clinical investigation will be conducted as described in the approved clinical investigation plan in accordance with the normal clinical practice. Any deviation from the normal clinical practice will be recorded and explained.

27. Clinical Investigation Termination

- Regular Termination of the clinical investigation

The observational study completion date is the date on which the last subject is examined or receives an intervention for the purpose of final data collection, if the observation period for this subject is completed according to the clinical investigation plan.

- Premature Termination of the clinical investigation

The Sponsor and Investigator reserve the right to terminate the observational study at any time. Reasons for discontinuation must be documented appropriately.

Upon completion of the clinical investigation, the patients will be ensured medical care at the same clinical site, according to the times and procedures required by normal clinical practice.

28. Financing of the Clinical Investigation

The financial aspects of this clinical investigation are described in detail in the contract between Sponsor and CRO and between CRO and clinical site involved in this study.

29. Clinical Investigation Report

The final Clinical Investigation Report will be written by the CRO and then approved by “Sponsor”, and the Principal Investigator. It will be written in compliance with the ISO: 14155:2020, EU Regulation 745/2017 (Annex XV) and GDPR for both content and format.

30. Publication policy

The Sponsor agrees that the clinical results (including negative and inconclusive as well as positive results) can be made publicly available by the Investigator publishing in peer reviewed journals; presenting results at scientific congresses; and posting information and results on internet-based public registers and databases.

In any case, study results will be communicated in full to the competent Authorities by the submission of a complete Clinical Study Report.

As the Sponsor agrees that the study results can be published by the Investigator(s), the Investigator agrees to submit any manuscript (abstract, publication, paper etc.) to the Sponsor before any public disclosure.

This will be done in order to ensure that clinical trial results are reported in an objective, accurate and balanced manner. The Sponsor reviews proposed manuscripts prior to submission within a reasonable period of time (30-90 business days in relation with the complexity of the work).

The Investigator(s) will also be provided by the Sponsor with the clinical study report and the results of any additional analysis, tables, figures etc. undertaken for the purposes of the article, in order to take responsibility for the content of the publication(s).

On an exceptional basis, the Sponsor may temporarily delay registration of certain data elements (e.g. compound, name, outcome, measures etc.) to seek necessary intellectual property protection. This is because early disclosure of such a data could, in some circumstances, prevent or negatively impact patentability.

REFERENCES

2. Lemp MA. Advances in understanding and managing dry eye disease. *Am J Ophthalmol.* 2008; 146:350–6.
4. Bron A. et al., TFOS DEWS II Pathophysiology report. *Ocul Surf* 2017; 15:438-510

1. CHANGE HISTORY RECORD

1.1. Statistical Analysis Plan

Statistical Analysis Plan version	Statistical Analysis Plan date	Description of changes	Amendment version	Amendment date
1	October 10 th 2023	First version	-	-

1.2. Clinical Investigation Plan

Clinical Investigation Plan version	Clinical Investigation Plan date	Description of changes	Amendment version	Amendment date
1	October 10 th 2022	First release	-	-
2	March 14 th ,2023	Second release	052/SI Hyalistil Bio PF Mono/EM version 1 of March 14 th ,2023	March 14 th ,2023

1.3. CRF

CRF version	CRF date	Description of changes	Amendment version	Amendment date
1.0	March 9 rd 2023	First release	-	-
2.0	May 29 th , 2023	Second release		
3.0	July 24 th , 2023	Third release		

2. RATIONAL AND BACKGROUND

Dry eye disease (DED) is a common clinical problem as over 7 million people in the United States experience dry eye symptoms. Symptoms of DED include a sensation of dry eyes, foreign body sensation, irritation, burning, tearing, ocular pain, and itching, among others. DED affects quality of life and work productivity, and patients with moderate to severe DED may experience reduced visual function in addition to ocular dysfunction.

DED is a multi-factorial disease, defined by a loss of homeostasis of the tear film and accompanied by ocular symptoms, in which tear film instability and hyper-osmolarity, ocular surface inflammation and damage, and neuro-sensory abnormalities play etiological roles.

Hyalistil BIO PF (listed in the Medical Device Technical File as HA MONO 0.2% Phosp. Free-) is sterile medical devices (eye drops) for ophthalmic use containing 0.2% sodium hyaluronate. The device is presented in unidose containers phosphate-free. Therefore, HA MONO 0.2% Phosp. Free- is indicated to lubricate and hydrate the ocular surface able to provide a stable coating on the surface of the eye performing a moisturizing and lubricating action on the ocular surface, thus allowing a temporary relief to burning, irritation and all dry-eye related discomfort.

In addition, the device assures the protection of the ocular surface during the healing processes. Moreover, since the presence of phosphates in ophthalmic formulations may rarely cause, in patients with compromised cornea, corneal deposits or corneal opacities [1,2], HA MONO 0.2% Phosp. Free- is a specific formulation without phosphates (and alternative buffer systems) mainly indicated in all cases of ocular discomfort and ocular dryness due to (as example) dry eye syndrome, ocular surgery, allergy, environmental factors (sun exposure, wind, smoke, pollution, conditioned air), excessive use of computer monitors, contact lenses use, aging, Moreover, they protect the ocular surface during the process of wound healing after corneal abrasions.

One-two drops of HA MONO 0.2% Phosp. Free- should be instilled in the conjunctival fornix three to four times daily, unless otherwise indicated.

No safety concerns have been identified and reported on the leaflet with the exception of occasional burning and local irritation upon instillation.

Under these premises, considering that HA-MONO-0.2%-Phosp.free was marketed in Italy with the name “Hyalistil Bio PF”, the purpose of this prospective observational investigational plan is to assess the clinical performance, tolerance, and safety of Hyalistil Bio PF device after 35 ± 4 days of treatment in patients affected by eye *discomfort* in particular in case of ocular dryness.

3. CLINICAL INVESTIGATION OBJECTIVES

3.1. Primary objective

- Evaluation of Tear film break-up time with fluorescein (TFBUT) at Study Termination Visit (*Day 35 ± 4 of treatment*) compared to Visit 1 (*Day 0 of treatment - baseline*).

3.2. Secondary objective

The secondary objectives were:

Clinical Performance

- Evaluation of the change in total score (score from 6 to 33, considering a normal score 0-33) resulting from the sum of the corneal staining score (score from 0 to 15) and conjunctival staining score (score from 0 to 18) with fluorescein using the National Eye Institute Scale (NEI) at Visit 2 (*Day 14 ± 2 of treatment*) and at the Study Termination Visit (*Day 35 ± 4 of treatment*) compared to Visit 1 (*Day 0 of treatment - baseline*);
- Evaluation of the tear film stability per group as objectified by the tear break up time with fluorescein (TFBUT) at Study Termination Visit (*Day 35 ± 4 of treatment*) compared to Visit 2 (*Day 14 ± 2 of treatment*).
- Changes about Best Corrected Visual Acuity (BCVA) measured by the “*Early Treatment Diabetic Retinopathy Study*” (ETDRS) at Visit 2 (*Day 14 ± 2 of treatment*) and Study Termination Visit (*Day 35 ± 4 of treatment*) compared to Visit 1 (*Day 0 of treatment – baseline*).

Patient reported outcomes

- To compare patients reported outcomes (PRO) measures per group, including:
 - Patient's reported symptoms (SANDE) at Visit 2 (*Day 14 ± 2 of treatment*) and Study Termination Visit (*Day 35 ± 4 of treatment*) compared to Visit 1 (*Day 0 of treatment – baseline*).
 - Evaluation of the degree of satisfaction to the treatment reported by patients through the use of the visual analogue scale (VAS) ##, at the Study Termination Visit (*Day 35 ± 4 of treatment*).
 - Assessment of the quality of life (QOL) ### by “Questionnaire about Eye Symptoms and Daily Life” (DEQS) at Study Termination Visit (*Day 35 ± 4 of treatment*) compared to Visit 1 (*Day 0 of treatment - baseline*).

3.3. Safety Evaluations

- Evaluation of safety of daily instillation of ophthalmic solution during all the study period through:
 - ✓ Investigator Global Assessment of Safety (IGAS): using the 4-point scale: 1 = very good safety, 2 = good safety, 3 = moderate safety and 4 = poor safety. IGAS was evaluated at the Study Termination Visit. [Time Frame: Study Termination Visit];
 - ✓ Evaluation of reported adverse events/incidents. [Time Frame: During the treatment period];
 - ✓ Evaluation of intraocular pressure (IOP) [Time frame: Visit 1, Visit 2 and Study

Termination Visit];

According to clinical practice, the Investigator will perform all clinical evaluations on both eyes of the individual patient.

In the case that both eyes are affected by ocular dry eye, the statistical analysis will be performed considering the eye with the lowest level of TFBUT score “worse eye”. If the level of TFBUT score at baseline is the same in both eyes, then the eye with the highest level of NEI score will be designated as the “worse eye”. If the level of NEI score at baseline is the same in both eyes, then the right eye will be designated as the “worse eye.”

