14.4 Name or number of the model/type to permit full identification

The name of the model to permit full identification of the medical devices is: **Hyalistil Bio PF**.

15. Investigational medical device storage and handling

The Sponsor will offer, like free samples, individual boxes containing an adequate supply of the investigational product to be instilled during the study to each subject.

The Pharmacist and/or Investigator will be responsible for receipt, proper storage, and usage of experimental product, as well as for the investigational product distribution, collection of used and unused vials and final disposal of the remaining investigational product.

The investigational product must be stored not exceeding 25 °C at the investigational sites, in an appropriate locked room accessible only to the pharmacist, the Investigator, or a duly designated person.

A temperature probe and data logger will accompany the investigational product on shipment. It is essential that the investigational sites verify the temperature excursion during shipment against acceptable storage conditions in order to identify potential stability concerns during shipment. These must be immediately communicated to the Sponsor that will decide upon appropriate actions to be taken. The investigational product will be stored in a locked place, sheltered from light.

PI, or a delegate, will maintain an inventory record of the investigational product received.

At the conclusion of the study, a final medical device accountability will be performed. If any supplies are missing, this will be indicated together with an explanation for the discrepancy.

During the Visit 1 the study personnel will give the patient boxes containing the investigational product.

Patient should bring the investigational product, boxes containing for 35±4 days of treatment, at home and store not exceeding 25 °C.

As previously described, each single-dose container must be used immediately after opening.

Do not touch the end of the open container and do not put it in direct contact with the eye.

Each single-dose container has the amount needed to treat both eyes.

Any residue must not be reused, as **Hyalistil Bio PF** does not contain preservatives and the remaining product could become contaminated, exposing to the risk of eye infections.

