5.3. Safety Endpoints

Evaluation of safety parameters

Evaluation of safety of daily instillation of ophthalmic solution during all the study period through:

- Evaluation of safety of daily instillation of ophthalmic solution during all the study period through:
 - Investigator Global Assessment of Safety (IGAS): using the 4-point scale: 1= very good safety, 2 =good safety, 3 = moderate safety and 4 = poor safety. IGAS will be evaluated at the Study Termination Visit. [Time Frame: Study Termination Visit];
 - Evaluation of reported adverse events/incidents. [Time Frame: During the treatment period].
- Evaluation of intraocular pressure (IOP) [Time frame: Visit 1, Visit 2 and Study Termination Visit];
- Evaluation of *compliance* through verification of correct instillation of the medical device,

Study code: 052/SI Hyalistil Bio PF Mono

counting of single dose containers and boxes. [Time Frame: Visit 2 and Study Termination Visit].

[^]According to clinical practice, the Investigator will perform all clinical evaluations on both eyes of the individual patient.

The statistical analysis will be performed considering right eye as the “study eye.”

#The primary end point will be evaluated on the ITT population and in PP population.

†The TFBUT value will be recorded as the average of 3 measurements.

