9. GENERAL ISSUES FOR STATISTICAL ANALYSIS

9.1 Definitions, Derived Variables and Datasets

Variable (CRF)	Variable	Type	Description
md_dispensing_q7; checkcomp_and_mdret_q3.	Treat_time	Continuous	Treatment duration
age	Age	Continuous	Age
sex_at_birth	Sex	Discrete	Sex
race	Race	Discrete	Race
eoq_q3; eoq_q4;	Ext_oc_ex	Discrete	External ocular examination
mh_part1_q1; mh_part1_q1_ongoing; mh_part1_q2; mh_part1_q2_ongoing; mh_part1_q3; mh_part1_q3_ongoing; mh_part1_q4; mh_part1_q4_ongoing; mh_part1_q5; mh_part1_q5_ongoing; mh_part1_q6; mh_part1_q6_ongoing; otherprevious_cdiseases; table_otherprevious_cd1.	Med_hist	Discrete	Medical history
concomitant_q1; concomitant_q2; concomitant_q3;	Conc_med	Discrete	Concomitant medications

Hyalistil Bio PF Mono
Medical device

Study code: 052/SI Hyalistil Bio PF Mono

concomitant_q4.			
tfbut_q2_od; tfbut_q3_od; tfbut_q4_od; tfbut_q2_os; tfbut_q3_os; tfbut_q4_os; tfbut_q5_od_a; tfbut_q5_os_a.	TFBUT	Continuous	Tear film break-up time with fluorescein
cornea_od_totalscore_a; cornea_os_totalscore_a; conjunctiva_od_totalscore_c; conjunctiva_od_totalscore_d; cornea_conjunctiva_os_b_d; cornea_conjunctiva_od_a_c;	NEI_total NEI_cornea NEI_conjunt	Continuous	National Eye Institute Scale
eo5;	BCVA	Continuous	Best Corrected Visual Acuity
sande_q3_severity; sande_q4_frequency; sande_qc_score2;	SANDE_total SANDE_sev SANDE_freq	Continuous	Symptom Assessment in Dry Eye
vasscale_q2; vasscale_cornea_q1; vasscale_cornea_q2; vasscale_cornea_q3; vasscale_cornea_q4; vasscale_cornea_q5;	VAS1 VAS2 VAS3 VAS4 VAS5	Continuous	Degree of satisfaction to the treatment
sensazione_deqs; secchezzaoculare; doloreagliocchi; stanchezzaoculare; pesantezzadellepalpedre; rossoreagliocchi; sensazione_deqs_1; secchezzaoculare_1; doloreagliocchi_1; stanchezzaoculare_1; rossoreagliocchi_1; deqs_q13; deqs_q14; deqs_q15; deqs_3. GES	DEQS_sum_score DEQS_subscale1 DEQS_subscale2	Continuous	Questionnaire about Eye Symptoms and Daily Life
igas_q1	IGAS	Discrete	(Investigator Global Assessment of Safety)

Study code: 052/SI Hyalistil Bio PF Mono

Incident_adverseevent_q1; incident_adverseevents_q2; incident_adverseevent_q3; endofstudy2_q4;	Adv_event_Inc	Discrete	Adverse events/incidents
iop_q2_od; Iop_q2_os;	IOP	Continuous	Evaluation of intraocular pressure
checkcompliance_q1; checkcompliance_q2; checkcompl_and_mdret_q3;	Compliance	Continuous/Discrete	Evaluation of compliance through verification of correct instillation of the medical device

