Subscale scores will be calculated similarly, using only the item from each subscale.

- GENERAL EYES STATUS (GES) will be summarized as minimum, maximum, mean, standard deviation or median and IQR. Paired t-test or Wilcoxon signed-rank test will be used to test the statistical significance of the change from baseline to the study termination. [Time frame: Visit 1 and Study Termination Visit].

GENERAL EYES STATUS will be assessed using the degree scores of a question answered using the 6-point scale:1= Estremamente bene, 2 = Molto bene, 3 = Bene, 4 = Male, 5= Molto male and 6= Estremamente male.

Safety Evaluation:

- IGAS will be summarized reporting the number of patients and related percentage in each category. [Time frame: Study Termination Visit].

The Safety of medical device will be assessed using the Investigator Global Assessment of Safety (IGAS): using the 4-point scale:1= very good safety, 2 =good safety, 3 = moderate safety and 4 = poor safety. IGAS will be evaluated during the Study Termination Visit. [Time Frame: Study Termination Visit].

- Incidents will be coded using the last updated version of the MedDRA dictionary to give a preferred term (PT) and a system/organ class term (SOC) for each event. The number of patients who experienced at least one incident, study product-related incidents, serious incidents, and the number of patients withdrawn due to an incident will be summarized. The frequency of incidents will be presented overall, by SOC and PT, and additional grouping by severity and relationship to the observed treatment will be performed. [Time Frame: During the treatment period].

- Changes from baseline in IOP will be summarized as minimum, maximum, mean, standard deviation or median and IQR. Paired t-test or Wilcoxon signed-rank will be used to test the statistical significance of the change from baseline to each timepoints. [Time frame: Visit 1, Visit 2 and Study Termination Visit].

Intraocular pressure (IOP) measurement was performed using a Goldmann applanation tonometer after topical anesthesia with unpreserved 0.4% oxybuprocaine hydrochloride.

Moreover, for each endpoint, a delta % calculation will be performed.

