IGAS		
	N	%
1 very good safety	x	x.xx
2 good safety	x	x.xx
3 moderate safety	x	x.xx
4 poor safety	x	x.xx

Program SAS 9.4 ('Local', X64_10HOME) date xxXXXXxxx

Study code: 052/SI Hyalistil Bio PF Mono

Table 5.13.1 IOP Intraocular Pressure, ITT population (v1) vs (v3)

ITT population

IOP v1 vs v3

Variable IOP Visit 1

Test for Normality							
Test	Statistic		P-value				
Shapiro-Wilk	W	x.xxxx	Pr < W		x.xxxx		
Kolmogorov-Smirnov	D	x.xxxx	Pr > D		x.xxxx		
Cramer-von Mises	W-Qu	x.xxxx	Pr > W-Qu		x.xxxx		
Anderson-Darling	A-Qu	x.xxxx	Pr > A-Qu		x.xxxx		
N	Mean	Std dev	Min	Max	Lower quartile	Median	Upper quartile
x	x.xx	x.xx	x.xx	x.xx	x.xx	x.xx	x.xx

Variable: IOP Visit 3

Test for Normality							
Test	Statistic		P-value				
Shapiro-Wilk	W	x.xxxx	Pr < W		x.xxxx		
Kolmogorov-Smirnov	D	x.xxxx	Pr > D		x.xxxx		
Cramer-von Mises	W-Qu	x.xxxx	Pr > W-Qu		x.xxxx		
Anderson-Darling	A-Qu	x.xxxx	Pr > A-Qu		x.xxxx		
N	Mean	Std dev	Min	Max	Lower quartile	Median	Upper quartile
x	x.xx	x.xx	x.xx	x.xx	x.xx	x.xx	x.xx

Hyalistil Bio PF Mono
Medical device

Study code: 052/SI Hyalistil Bio PF Mono

Variable: Difference IOP Visit 3 – Visit 1

Basic Statistical Measures

Location	Variability		
Mean	x.xx	Std dev	x.xx
Median	x.xx	Variance	x.xx
Mode	x.xx	Range	x.xx
Interquartile range		x.xx	

Location test: Mu0=0

Test	Statistic	P-value
Student's T	t	x.xxx
sign	M	xx
Signed rank	S	x.xxx

Program SAS 9.4 ('Local', X64_10HOME) date xxXXXXxxx

Study code: 052/SI Hyalistil Bio PF Mono

Table 5.14.1 IOP Intraocular Pressure, ITT population (v1) vs (v2)

ITT population

IOP v1 vs v2

Variable IOP Visit 1

Test for Normality							
Test		Statistic		P-value			
Shapiro-Wilk	W	x.xxxx	Pr < W	x.xxxx			
Kolmogorov-Smirnov	D	x.xxxx	Pr > D	x.xxxx			
Cramer-von Mises	W-Qu	x.xxxx	Pr > W-Qu	x.xxxx			
Anderson-Darling	A-Qu	x.xxxx	Pr > A-Qu	x.xxxx			
<hr/>							
N	Mean	Std dev	Min	Max	Lower quartile	Median	Upper quartile
x	x.xx	x.xx	x.xx	x.xx	x.xx	x.xx	x.xx
<hr/>							

Variable: IOP Visit 2

Test for Normality							
Test		Statistic		P-value			
Shapiro-Wilk	W	x.xxxx	Pr < W	x.xxxx			
Kolmogorov-Smirnov	D	x.xxxx	Pr > D	x.xxxx			

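### The one-study-eye rule has no exception for safety, so where both eyes are affected the second treated eye's IOP is measured but is not in the planned IOP summaries

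*SAP*

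**What the plan says.** **The eye rule.** SAP 3.3 lists the global safety assessment, adverse events and IOP as the safety evaluations. It then says that "the Investigator will perform all clinical evaluations on both eyes of the individual patient" and that, with both eyes affected, "the statistical analysis will be performed considering the eye with the lowest level of TFBUT score" (the worse eye; ties go to the higher NEI score, then to the right eye). The same rule closes SAP 5.2. SAP 5.3, where IOP is a safety endpoint, closes with a different one: "The statistical analysis will be performed considering right eye as the" study eye. The Protocol has the same split: worse eye in the synopsis, right eye in section 19.

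**Treatment and measurement.** Protocol 6 admits patients with one or both eyes affected, and Protocol 14.1 directs the drops to the affected eye. Protocol 15 adds: "Each single-dose container has the amount needed to treat both eyes". IOP is part of the examination of both eyes at all three visits (SAP 4.1).

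**Analysis.** SAP 9.1 maps the right and left fields ("iop_q2_od; Iop_q2_os") to a single variable, IOP. SAP 13.2 says: "Changes from baseline in IOP will be summarized as minimum, maximum, mean, standard deviation or median and IQR", with a paired test at each timepoint. SAP 15.2 lists two IOP tables, 5.13.1 and 5.14.1. Neither is split by eye, and both are labelled ITT.

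**The Protocol's safety commitment.** Protocol section 25, Safety Data Evaluation, says that all safety data from medical examinations are entered in the eCRF, summarised descriptively and reported.

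**The concern.** Analysing one eye per patient is a normal way to avoid within-patient correlation in a performance endpoint, and choosing the eye with the shortest baseline TFBUT suits an endpoint that measures TFBUT. Neither reason carries over to safety. In a patient with both eyes affected, both eyes receive the device, and baseline tear stability does not make one of them less relevant to a pressure change.

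IOP is the only quantitative ocular measurement among the SAP's safety endpoints. If the eye rule governs it, the report could describe IOP as unchanged on the basis of some of the exposed eyes, while readings from the others sit unsummarised in the database. A mean change in the study eye cannot show a rise confined to the fellow eye.

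**Working it through.** **1. Does the rule reach IOP?** Set side by side:

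| Place | Eye rule | IOP in the same block? | Safety exception? |
|---|---|---|---|
| SAP 3.3 Safety Evaluations | worse eye | yes | none |
| SAP 5.3 Safety Endpoints | right eye | yes | none |
| Protocol synopsis, Endpoints | worse eye | yes | none |
| Protocol 19 | right eye | yes | none |

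In SAP 5 the footnote marker is on the heading of the whole section, which includes 5.3. In the Protocol synopsis it is on the whole endpoint block. All four places speak of the statistical analysis in general.

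**2. What enters the IOP tables?** Two fields per patient per visit are captured, one variable is defined, and each visit comparison has one unsplit table. No per-eye or either-eye summary is listed. That each patient contributes one value follows from the eye rule; the table shells do not say so.

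**3. Size.** The plan gives no figure on this point. The one planned number used is the enrolment of N = 28 (SAP 7). Let p be the share of patients with both eyes affected. The documents do not state it, so it is an assumption.

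- Treated eyes = 28 + 28p = 28(1 + p)
- Treated eyes not summarised under the worse-eye rule = 28p
- Share not summarised = 28p / [28(1 + p)] = p/(1 + p)

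| Assumed p | Treated eyes | Not summarised | Share |
|---|---|---|---|
| 0.2 | 33.6 | 5.6 | 17% |
| 0.5 | 42 | 14 | 33% |
| 0.8 | 50.4 | 22.4 | 44% |
| 1.0 | 56 | 28 | 50% |

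**4. The right-eye version.** It drops the treated left eye of each patient with both eyes affected, so 28p eyes are again lost. A patient with only the left eye affected would also contribute an untreated right eye to the IOP result and lose the treated one. Under this version p/(1 + p) is therefore a lower bound.

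**5. Population.** SAP 8.5 assigns all safety analyses to the safety population, but both IOP tables are labelled ITT.

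**The case against.** The strongest reply is that the rule was never meant for safety. Selecting by TFBUT and then NEI is a performance criterion, the same text closes SAP 5.2, and the heading of SAP 5 speaks of primary and secondary outcomes. No sentence says that IOP is analysed in the study eye only. SAP 10.1 says that all data are summarised and listed as appropriate, SAP 15 says that its table list may be incomplete, and Protocol section 25 promises summaries of all safety examination data.

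Part of this stands. The intention may well be broader than the text, and fellow-eye readings might be listed. But the general promises do not cancel a specific eye rule stated in both safety sections. Protocol section 25 conflicts with that rule and does not repair it. The mock listings name no IOP variable, and a listing is not a summary. If the tables were instead meant to pool all eyes, the eye rule would be contradicted and the paired test would treat two eyes of one patient as independent. The text needs correcting on either reading.

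A reader might infer more than the documents support:

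- **That the fellow eyes go unexamined.** They are examined at every visit; what is missing is their place in the summary.
- **That a pressure rise in the fellow eye would appear nowhere.** Adverse events are tabulated per patient with no eye restriction, so a rise recorded as one would be counted.
- **That visual acuity is lost in the same way.** BCVA is a secondary performance endpoint, where a one-eye rule can be defended, and SAP 15.2 lists no BCVA table for either eye.

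The background sections of both documents report no safety concern beyond occasional burning and local irritation. That limits the urgency but does not justify omitting exposed eyes.

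**Conclusion.** The concern holds for IOP. As written, the one-eye rule applies to safety, and under either version the IOP of the second treated eye is measured and captured but is not in the planned summaries when both eyes are affected. This is at odds with Protocol section 25.

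Under the worse-eye rule the share of treated eyes not summarised is p/(1 + p): 17%, 33% and 50% at assumed p of 0.2, 0.5 and 1.0. It would be tempting to say that a third to a half of exposed eyes are omitted. That requires at least half of the patients to have both eyes affected, which the documents do not say.

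The conclusion rests on two inferences: that both eyes are treated when both are affected (Protocol 14.1 and 15), and that the eye rule means what its placement and general wording say. Adverse events and the global safety assessment are not restricted by eye. The primary endpoint and the sample size are not affected.

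**What to change.** In SAP 3.3 and 5.3, state that the study-eye rule applies to performance endpoints only, and reconcile the worse-eye and right-eye versions there, in SAP 5.2 and in the Protocol synopsis and section 19.

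For IOP:

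- Summarise the value and its change from baseline at each visit for treated right eyes and treated left eyes separately. Each summary then has at most one eye per patient, so no correlation has to be modelled.
- Use the safety population of SAP 8.5 and relabel Tables 5.13.1 and 5.14.1 accordingly.
- Add the largest IOP increase from baseline in any treated eye, one value per patient, with a by-patient listing. As a maximum of noisy readings it is biased upward, more so with two eyes than with one, so it should be read descriptively and not tested.

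The cost is SAP wording and one or two extra tables. The right-eye and left-eye IOP fields already exist, so no new data are needed.
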